Montanide-ISA-51 in combination with poly-ICLC and synthetic over-lapping long peptides from NY-ESO-1 has been administered to 11 patients with ovarian, fallopian tube, or primary peritoneal cancer in a phase I clinical trial. This vaccine was generally well-tolerated with grade 1-2 injection site reactions and fatigue as the only adverse events that were considered possibly or definitely drug-related¹⁸. No grade 3 or 4 adverse events were reported. In another clinical trial (ClinicalTrials.gov Identifier NCT01079741) 19 patients with high-risk melanoma received Montanide –ISA-51 combined with poly-ICLC and NY-ESO-1 protein given s.q. every 3 weeks for 4 doses. The vaccine was generally well-tolerated with grade 1 and 2 injection site reactions and transient, grade 1 or 2, flu-like symptoms that resolved after 12-48 hours⁶³.

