5.5 Definition of Dose-Limiting Toxicity

Dose-limiting toxicity (DLT) is based on the CTEP Active Version (version 5.0) of the NCI Common Terminology Criteria for Adverse Events (CTCAE). DLT refers to toxicities experienced within 42 days (6 weeks of Neoantigen Vaccine treatment initiation i.e. 2 vaccinations “DLT window”). If treatment has to be delayed because of a toxicity that does not fulfill the criteria of a DLT, the DLT window should be extended by that time period of delay. A DLT will be defined as follows:

1. Grade 3 or 4 toxicity that is definitely, probably, or possibly related to the administration of vaccine, excluding:
 - Transient (\leq 72 hours) flu-like symptoms
 - Grade 3 nausea, vomiting, diarrhea, or constipation that returns to grade 2 (or lower) level within 48 hours
 - Any grade 3 rash that resolves to grade 2 or grade 1 within \leq 14 days
 - Any grade 3 endocrine abnormality that is corrected with hormonal therapy within 4 weeks
2. Grade 3 or 4 abnormal laboratory value that is definitely, probably, or possibly related to the administration of vaccine if it persists for more than 7 days, or requires hospitalization or medical intervention excluding:
 - Any grade 3 electrolyte abnormality:
 - lasts \leq 72 hours,
 - is not clinically complicated,
 - and resolves spontaneously or responds to conventional medical intervention
3. Any grade 3 or grade 4 toxicity that is considered, in the opinion of the Principal Investigator, to be dose-limiting.
4. Any death related to study treatment.

Management and dose modifications associated with the above adverse events are outlined in Section 6 (Expected Toxicities and Dosing Delays/Dose Modifications).

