6.3.2 NeoVax plus Montanide

6.3.2.1 If a participant develops grade 3 toxicity attributable to the vaccine, additional treatment will be withheld until the toxicity has resolved or improved to grade 1. If the toxicity constitutes a DLT as defined in 5.6, the participant will be removed from the study. If the toxicity does not fulfill the criteria of a DLT, the next vaccine administration may be delayed for a maximum duration of 14 days. If vaccine dosing has to be delayed more than 2 times because of an attributable toxicity that is not considered a DLT, the participant will be removed from the study

6.3.2.2 If a participant develops grade 4 toxicity attributable to the vaccine s/he will be removed from treatment

6.3.2.3 If two or more grade 4 or greater toxicities attributable to the vaccine are observed, the trial will be suspended to investigate the causes of these (unexpected) toxicities

6.3.2.4 Vaccine dosing may be delayed in the event of unrelated adverse events if it is felt to be in the medical best interest of the patient following discussion by the treating investigator with the study Principal Investigator or designee. Vaccine dosing may be resumed once the treating investigator deems it is medically safe to do so following discussion with the study Principal Investigator or designee as long as the participant has not developed progressive disease

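### The DLT exclusion for transient flu-like symptoms has no grade 3 limit, so a short non-fatal grade 4 event classed as flu-like is a DLT only at the Principal Investigator's discretion

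*Protocol*

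**What the plan says.** Protocol 5.5 gives four routes to a DLT.

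- **Item 1** counts any "Grade 3 or 4 toxicity that is definitely, probably, or possibly related to the administration of vaccine, excluding" four listed kinds of event. The first exclusion, for transient events, ends with "72 hours) flu-like symptoms": it sets a duration and no grade. The other three (gastrointestinal, rash, endocrine) each name grade 3.
- **Item 2** counts a related grade 3 or 4 laboratory value "if it persists for more than 7 days, or requires hospitalization or medical intervention excluding" certain electrolyte changes. That exclusion opens with "Any grade 3 electrolyte abnormality" and applies only if the abnormality lasts 72 hours or less, "is not clinically complicated", and resolves by itself or with conventional treatment.
- **Item 3** is discretionary: "Any grade 3 or grade 4 toxicity that is considered, in the opinion of the Principal Investigator, to be dose-limiting".
- **Item 4** covers treatment-related death.

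The SAP (Design) takes its DLT definition from 5.5 and adds no grade limit. Protocol 13.1 and the SAP let a cohort pass with at most one DLT in five patients. Protocol 5.4.3 and 13.1 also require at least two vaccinations, without a DLT, to complete the observation period successfully.

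Separate rules govern grade 4 events. Under 6.3.2.2, "If a participant develops grade 4 toxicity attributable to the vaccine s/he will be removed from treatment". Section 6.3.2.3 suspends the trial after two or more vaccine-attributable toxicities of grade 4 or above. Section 6.5 requires discontinuation for most drug-related grade 4 events.

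**The concern.** The flu-like exclusion sits under a parent clause that covers grades 3 and 4, so without its own grade limit it removes both. The electrolyte exclusion has the same 72-hour limit, but it is confined to grade 3 and to uncomplicated events. The flu-like one has neither safeguard.

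The category is also broad. Protocol 7.8.1.1 and 7.8.1.2 list fever, dizziness, raised blood pressure, raised pulse and shortness of breath among flu-like symptoms. Section 7.8.1.2 gives several of the same signs for hypersensitivity. The label given to a short, severe reaction after vaccination can therefore decide whether item 1 applies.

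At stake is the DLT count: it is the primary endpoint, and in a cohort of five one patient can separate 1/5 (pass) from 2/5 (fail).

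**Working it through.** **1. The five exclusions side by side (Protocol 5.5)**

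| Exclusion | Grade limit | Time condition | Further condition |
|---|---|---|---|
| Flu-like (item 1) | none | 72 hours or less | none |
| Gastrointestinal (item 1) | grade 3 | down to grade 2 or lower within 48 hours | none |
| Rash (item 1) | grade 3 | down to grade 2 or 1 within 14 days | none |
| Endocrine (item 1) | grade 3 | corrected within 4 weeks | hormonal therapy |
| Electrolyte (item 2) | grade 3 | 72 hours or less | uncomplicated; resolves by itself or with conventional treatment |

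Four of five carry a grade 3 limit.

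**2. Route of a non-fatal grade 4 flu-like event of 72 hours or less**

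- Item 1: excluded.
- Item 2: laboratory values only. An accompanying laboratory abnormality could qualify, but as a separate event.
- Item 4: deaths only.
- Item 3: the only route left.

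Sections 6.3.2.2, 6.3.2.3 and 6.5 act on treatment and on the trial; none makes the event a DLT.

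**3. The plan's own figures**

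The probability that a cohort of five passes is (1−p)^5 + 5p(1−p)^4. At p = 10, 20, 30, 40, 50 and 60% this gives 91.9, 73.7, 52.8, 33.7, 18.8 and 8.7%. The table in 13.1 and the SAP states 92, 74, 53, 34, 19 and 9%, so it is reproduced. In that table p is the rate of DLTs as 5.5 defines them.

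**4. Timing of the event**

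Vaccinations 1 and 2 fall at weeks 12 and 15 (Protocol 5.2).

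- *After vaccination 1, before vaccination 2.* Removal under 6.3.2.2 leaves the patient with one vaccination, short of the minimum of two. The patient cannot complete the observation period successfully, yet is not a DLT under item 1. The documents do not say how this patient counts among the five, so no shift in the rate can be computed.
- *After vaccination 2, within the DLT window.* The two-vaccination minimum is met. With no other DLT and item 3 unused, the patient counts as one of five without a DLT.

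**5. Size in the second case**

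The cohort's DLT rate is lower by 1/5, or 20 percentage points. Let X be the number of DLTs among the other four patients, taken as Binomial(4, p), where p is an assumption. As written, the cohort passes if X ≤ 1. If the event counted, it would pass only if X = 0. The decision differs when X = 1, with probability 4p(1−p)^3.

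| Assumed p | Passes as written, P(X ≤ 1) | Passes if counted, P(X = 0) | Decision differs, P(X = 1) |
|---|---|---|---|
| 10% | 0.948 | 0.656 | 4 × 0.10 × 0.729 = 0.292 |
| 20% | 0.819 | 0.410 | 4 × 0.20 × 0.512 = 0.410 |
| 30% | 0.652 | 0.240 | 4 × 0.30 × 0.343 = 0.412 |

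All of these are conditional on the event having occurred, after vaccination 2, in a patient with no other DLT, with item 3 unused.

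**6. How likely the event is**

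The documents give no rate. Protocol 2.3.3 cites two trials of poly-ICLC with Montanide. In one (19 patients) it reports "transient, grade 1 or 2, flu-like symptoms that resolved after 12-48 hours"; in the other (11 patients), only grade 1-2 injection site reactions and fatigue were considered drug-related.

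**The case against.** The strongest case against has four parts.

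- **Item 3 would probably be used.** Section 7.2.2 describes grade 4 as life-threatening or disabling, and 5.7 and 5.10 require immediate notice to the Principal Investigator of life-threatening complications. The person who decides would know of the event, in a patient already taken off treatment. This stands as a reason to expect the gap rarely to matter. It still leaves the primary endpoint of an open-label trial to judgement where a written rule would do, and the Principal Investigator is also the study sponsor (7.3). No misuse is suggested.
- **The exclusion may be deliberate.** Ipilimumab is the escalated agent; the vaccine dose is constant (7.8.1.5). A passing reaction expected from the vaccine arguably should not set the ipilimumab dose. That is a fair reason to exclude grade 3 events. It is weaker for grade 4, which 6.3.2 treats as unexpected and treatment-ending whatever its duration.
- **Such events may not occur.** The dose-limiting fever in 2.3.2.4 arose at 6 mg/m² or more of poly-ICLC, against 2 × 0.5 mg here. The documents do not reproduce the CTCAE grade definitions, so which flu-like terms can reach grade 4 cannot be checked. This stands.
- **It is late to act, and the SAP already tabulates worst grade and relatedness.** Accrual has ended, so rewording 5.5 changes no decision in this trial. The planned table would show a related grade 4 event but does not cross it with the DLT flag.

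A reader might also infer that any use of duration to exempt a grade 4 event is an anomaly. It is not: item 2 does so for laboratory values, but keeps those that need hospitalization or medical intervention.

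**Conclusion.** The gap in the wording is real, and nothing in the protocol or SAP closes it. It affects what is counted, not patient management. A shift of 20 percentage points in the cohort rate, and a 29% to 41% chance of a different decision, apply clearly only to an event after the second vaccination and within the window, in a patient with no other DLT, with item 3 unused, at assumed DLT rates of 10% to 30% in the other four. If item 3 is used, nothing changes. Overall the effect may be zero, and the change is optional.

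Three stronger readings are not supported. A reader might infer that patients with such events go unprotected; 6.3.2.2, 6.3.2.3 and 6.5 provide removal, suspension and discontinuation. A reader might infer that the MTD or DLT rate is wrong; the documents report no such event. A reader might take 29% to 41% as the chance that the trial's decision was wrong, or apply it to any event in the window; it is conditional as stated, and for an event after the first vaccination the documents do not settle how the patient counts.

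**What to change.** Reword the bullet in 5.5 to: *Transient (72 hours or less) grade 3 flu-like symptoms*. This also keeps the gap out of any later protocol built on this one.

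Because accrual stopped when the MTD was determined (SAP, Modified Design), report the DLT rate as defined and do not redefine the endpoint after the fact. Add one SAP listing: every grade 4 event (C_toxgrd) at least possibly related to NeoVax (c_attrib 2, 3 or 4) within the DLT window that D_toxdlt does not flag, with the reason and the number of vaccinations received. If there are none, say so. State the window used, since 5.5 gives 42 days and 13.1 gives seven weeks.

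The cost is one bullet and one listing. Grade, attribution and DLT flag are already in the SAP (On-study Toxicities). The event onset date is not among the variables shown there and would have to be added, and the vaccination count must be brought in. The downside is that a DLT count under the grade limit could be slightly higher.

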6.4 Criteria to Resume Treatment

Subjects may resume treatment with Ipilimumab and NeoVax plus Montanide when the drug-related AE(s) resolve to Grade \leq 1 or baseline value, with the following exceptions:

- Subjects may resume treatment in the presence of Grade 2 fatigue
- Subjects who have not experienced a Grade 3 drug-related skin AE may resume treatment in the presence of Grade 2 skin toxicity
- Subjects with baseline Grade 1 AST/ALT or total bilirubin who require dose delays for reasons other than a 2-grade shift in AST/ALT or total bilirubin may resume treatment in the presence of Grade 2 AST/ALT OR total bilirubin

- Subjects with combined Grade 2 AST/ALT AND total bilirubin values meeting discontinuation parameters should have treatment permanently discontinued
- Drug-related pulmonary toxicity, diarrhea, or colitis, must have resolved to baseline before treatment is resumed
- Drug-related endocrinopathies adequately controlled with only physiologic hormone replacement may resume treatment

If the criteria to resume treatment are met, the subject should restart treatment at the next scheduled timepoint per protocol. However, if the treatment is delayed past the next scheduled timepoint per protocol, the next scheduled timepoint will be delayed until dosing resumes.

If treatment is delayed > 6 weeks, the subject must be permanently discontinued from study therapy, except as specified in discontinuation section.

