6.5 Discontinuation criteria

Treatment should be permanently discontinued for the following:

- Any Grade 2 drug-related uveitis or eye pain or blurred vision that does not respond to topical therapy and does not improve to Grade 1 severity within the re-treatment period OR requires systemic treatment
- Any Grade 3 non-skin, drug-related adverse event lasting > 7 days, with the following exceptions for drug-related laboratory abnormalities, uveitis, pneumonitis, bronchospasm, diarrhea, colitis, neurologic adverse event, hypersensitivity reactions, and injection reactions
 - Grade 3 drug-related uveitis, pneumonitis, bronchospasm, diarrhea, colitis, neurologic adverse event, hypersensitivity reaction, or injection reaction of any duration requires discontinuation
 - Grade 3 drug-related laboratory abnormalities do not require treatment discontinuation except those noted below
 - Grade 3 drug-related thrombocytopenia > 7 days or associated with bleeding requires discontinuation
 - Any drug-related liver function test (LFT) abnormality that meets the following criteria require discontinuation:
 - AST or ALT > 8 x ULN
 - Total bilirubin > 5 x ULN
 - Concurrent AST or ALT > 3 x ULN and total bilirubin > 2 x ULN
- Any Grade 4 drug-related adverse event or laboratory abnormality, except for the following events which do not require discontinuation:
 - Isolated Grade 4 amylase or lipase abnormalities that are not associated with symptoms or clinical manifestations of pancreatitis and decrease to < Grade 4 within 1 week of onset.

- Isolated Grade 4 electrolyte imbalances/abnormalities that are not associated with clinical sequelae and are corrected with supplementation/appropriate management within 72 hours of their onset
- Any dosing interruption lasting > 6 weeks with the following exceptions:
 - Dosing interruptions to allow for prolonged steroid tapers to manage drug-related adverse events are allowed. Prior to re-initiating treatment in a subject with a dosing interruption lasting > 6 weeks, the Principal Investigator must be consulted. Tumor assessments should continue as per protocol even if dosing is interrupted
 - Dosing interruptions > 6 weeks that occur for non-drug-related reasons may be allowed if approved by the Principal Investigator. Prior to re-initiating treatment in a subject with a dosing interruption lasting > 6 weeks, the Investigator must be consulted. Tumor assessments should continue as per protocol even if dosing is interrupted

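### Some toxicities that Sections 6.4 and 6.5 say must end treatment permanently are not DLTs, or not automatically DLTs, under Section 5.5, so dose decisions can miss them

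*Protocol*

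**What the plan says.** **What counts as a DLT.** Protocol Section 5.5 has four items. Items 1 and 2 cover grade 3 or 4 events at least possibly related to the vaccine. Item 3 adds "Any grade 3 or grade 4 toxicity that is considered, in the opinion of the Principal Investigator, to be dose-limiting". Item 4 is treatment-related death. Item 1 has exclusions, among them "Grade 3 nausea, vomiting, diarrhea, or constipation that returns to grade 2 (or lower) level within 48 hours" and "Any grade 3 endocrine abnormality that is corrected with hormonal therapy within 4 weeks".

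**What ends treatment.** Section 6.5 states: "Grade 3 drug-related uveitis, pneumonitis, bronchospasm, diarrhea, colitis, neurologic adverse event, hypersensitivity reaction, or injection reaction of any duration requires discontinuation". Section 6.3.1 has the same rule for nivolumab, with infusion reaction in place of injection reaction. Section 6.5 also lists "Any Grade 2 drug-related uveitis or eye pain or blurred vision that does not respond to topical therapy"; the rest of that sentence adds failure to improve to grade 1 within the re-treatment period, or a need for systemic treatment. Section 6.4 adds: "Subjects with combined Grade 2 AST/ALT AND total bilirubin values meeting discontinuation parameters should have treatment permanently discontinued".

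**What only delays treatment.** Under Section 6.3.2.1, a grade 3 vaccine toxicity that is not a DLT allows the next vaccination to be delayed by up to 14 days.

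**What drives the decisions.** Sections 5.4.1 and 13.1 move between dose levels and name the MTD on 0 or 1 DLT among 5 patients. Section 5.4.3 lets a participant complete the window with two vaccinations and no DLT. The SAP takes its primary endpoint from Section 5.5 as it stands, and its analysis section defines the DLT rate as the proportion with a DLT resulting from NeoVax.

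**The concern.** Excluding a short-lived event from the DLT definition makes sense when the patient can carry on with treatment. Here the protocol excludes an event as transient in one section and ends treatment for it in another. A third section implies that dosing may resume after a pause.

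The primary endpoint and the MTD are meant to say whether the combination can be tolerated at a given ipilimumab dose. If a patient has to stop all study treatment for drug-related toxicity inside the window and the DLT count does not move, the count understates intolerability. With five patients per cohort, one patient is 20 percentage points of the observed rate (1/5). One more event alongside a single DLT makes two, which reverses the decision. The SAP records that accrual stopped at the end of escalation, so there is no expansion cohort to correct an optimistic reading.

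**Working it through.** **1. The passages side by side**

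| Event | Section 5.5 | Sections 6.3.1 to 6.5 | Result |
|---|---|---|---|
| Grade 3 diarrhea, down to grade 2 within 48 hours | Excluded from item 1; a DLT only if the Principal Investigator invokes item 3 | If vaccine-related, a delay of up to 14 days (6.3.2.1); permanent stop at any duration (6.3.1, 6.5) | Direct conflict; DLT status is discretionary |
| Grade 2 uveitis, eye pain or blurred vision, either unresponsive to topical therapy and not improving to grade 1 within the re-treatment period, or needing systemic treatment | Not reachable: items 1 to 3 need grade 3 or 4, item 4 needs death | Permanent stop (6.3.1, 6.5) | Cannot be a DLT at that grade |
| Combined grade 2 AST/ALT and bilirubin meeting the discontinuation parameters | Not reachable, for the same reason | Permanent stop (6.3.1, 6.4) | Cannot be a DLT at that grade |
| Grade 3 endocrine event lasting more than 7 days | Excluded from item 1 if corrected with hormonal therapy within 4 weeks | 6.4 allows resumption if controlled with physiologic replacement; 6.5 stops grade 3 non-skin events over 7 days and lists no endocrine exception | Ambiguity between 6.4 and 6.5, not a clear forced stop |

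**2. How such a patient is counted.** Vaccinations fall at weeks 12, 15, 18 and 21, and Section 5.5 sets the window at 42 days. A patient vaccinated at weeks 12 and 15 and then stopped for one of the first three events before day 42 has two vaccinations. Unless item 3 is invoked for the diarrhea, that patient has no DLT and passes under Section 5.4.3. A patient stopped before the second vaccination does not complete the window, but the text does not say whether that patient counts against the dose or is replaced.

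**3. Reproducing the plan's figures.** With n = 5 and DLT rate p, P(clear) = P(X ≤ 1) = (1−p)^5 + 5p(1−p)^4. At p = 10, 20, 30, 40, 50 and 60% this gives 91.9, 73.7, 52.8, 33.7, 18.8 and 8.7%, which match the stated 92, 74, 53, 34, 19 and 9%. The arithmetic in Section 13.1 is correct; the issue is which events enter X.

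**4. Size under an assumed rate.** Let q be the proportion of patients permanently stopped inside the window for drug-related toxicity that is not a DLT, with no overlap with p. The documents give no value for q. Replacing p by p + q shows what the same rule would do if these patients were counted too. For p = 20%:

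- q = 0: 0.8^5 + 5(0.2)(0.8^4) = 0.3277 + 0.4096 = 73.7%
- q = 5%: 0.75^5 + 5(0.25)(0.75^4) = 0.2373 + 0.3955 = 63.3%
- q = 10%: 0.7^5 + 5(0.3)(0.7^4) = 0.1681 + 0.3602 = 52.8%
- q = 20%: 0.6^5 + 5(0.4)(0.6^4) = 0.0778 + 0.2592 = 33.7%

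Other DLT rates:

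| DLT rate p | q = 0 | q = 5% | q = 10% | q = 20% |
|---|---|---|---|---|
| 10% | 91.9% | 83.5% | 73.7% | 52.8% |
| 30% | 52.8% | 42.8% | 33.7% | 18.8% |

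**The case against.** DLT criteria and discontinuation rules serve different purposes and need not coincide. Items 1 and 2 of Section 5.5 look for vaccine-related events, while Section 6.5 covers any drug-related event, and patients have had 12 weeks of nivolumab before the first vaccination. Item 3 has no relatedness test and no exclusions, and an event that ends treatment is an obvious candidate for it. These events are also not hidden: Section 5.7 puts the reason and date of removal from therapy on the CRF, Section 7.2.2 puts potential drug-induced liver injury on SAE timelines, Section 12.2 has the monitoring committee review toxicity, and the SAP tabulates worst grades with attribution for each drug.

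The assumed rates may also be high. In the nivolumab plus peptide vaccine trial in Section 2.3.5.3 (49 patients), one patient had a DLT and the two others who stopped for toxicity did so after the 12-week DLT period. In the adjuvant trial in Section 2.3.5.4, 7.7% of nivolumab patients stopped for treatment-related events over all treatment. With q = 2% the clearing probability falls only from 73.7% to 69.6% (0.78^5 + 5(0.22)(0.78^4) = 0.2887 + 0.4072).

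Much of this stands. The grade 3 diarrhea case is not automatically a DLT, rather than never one. The size is uncertain, although neither comparison regimen included local ipilimumab, so both are indirect guides. What does not fall is the direct contradiction over short grade 3 diarrhea, and the two grade 2 triggers, which item 3 cannot reach. The general safety tables do not put these stops beside the DLT count on which the MTD rests.

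A reader might infer that every permanent-stop criterion escapes the DLT definition. That is not so: vaccine-related grade 3 pneumonitis or colitis falls under item 1. A reader might also infer that these patients should be counted as DLTs, or refused DLT-free status. That would redefine the primary endpoint after accrual stopped, and could charge nivolumab toxicity to an ipilimumab dose level.

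**Conclusion.** The conflict is real and should be fixed. For grade 3 diarrhea settling within 48 hours, the protocol gives three consequences that cannot all hold. For the two grade 2 triggers it ends treatment for events that cannot be DLTs at that grade. The endocrine wording is an ambiguity to resolve, not a further forced stop.

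The effect on dose decisions depends on a rate that the documents do not give. At a 20% DLT rate, and for an assumed 5 to 20% of additional non-overlapping stops inside the window, the 73.7% chance of clearing a cohort compares with 63.3% down to 33.7% if those patients were counted. This is an illustration, not an estimate.

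The documents do not show that any such case occurred, so they do not support the stronger inference that the MTD is wrong or that a cohort cleared improperly. They do show that a low DLT count alone cannot establish that patients were able to stay on the regimen.

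**What to change.** 1. **Protocol.** The clinical team should reconcile Sections 5.5, 6.3.1, 6.3.2, 6.4 and 6.5 so that each event has one stated consequence. No clinical rule is proposed here. The text should also say how a patient stopped for toxicity before the second vaccination is counted.
2. **SAP primary safety table.** Keep the Section 5.5 definition for the primary endpoint. Beside the DLT count, by ipilimumab dose level, report the number of patients permanently discontinued for drug-related toxicity inside the DLT window, with attribution to NeoVax, nivolumab and ipilimumab. Use the same window for both counts and state it, because Section 5.5 gives 42 days and Section 13.1 gives 7 weeks.
3. **MTD statement.** Qualify it with that count.

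The cost is wording and one table row. The reason and date of stopping are already required on the CRF (Section 5.7), and the SAP already lists attribution variables for each drug. Rewording cannot change escalation decisions already made, and the safety picture may look slightly less favourable.
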